4. [name]	Virologist, Lab. Sciences Division	Co-investigator
5. [name]	Scientist, Clinical Sciences Division	Co-investigator
6. [name]	Paediatric Surgeon, Shishu Hospital, Dhaka	Co-investigator
7. [name] [name]	Head, Progrm. Infect Dis & Vaccine Scien.	Co-investigator
8. [name] [name]	Director, ICDDR,B	Co-investigator

DESCRIPTION OF THE RESEARCH PROJECT

Hypothesis to be tested:

Concisely list in order, in the space provided, the hypothesis to be tested and the Specific Aims of the proposed study. Provide the scientific basis of the hypothesis, critically examining the observations leading to the formulation of the hypothesis.

1. Human rotavirus vaccine (RIX4414) is safe and immunogenic in infants

Specific Aims:

Describe the specific aims of the proposed study. State the specific parameters, biological functions/ rates/ processes that will be assessed by specific methods (TYPE WITHIN LIMITS).

Part 1 (Safety assessment in toddlers)

Primary

- For each vaccine concentration (10^5 and 10^6 ffu), to assess the safety and reactogenicity of a single oral dose of the rotavirus vaccine *versus* placebo in healthy children 2-4 years old.

Secondary

- To assess viral shedding in each study group.

Part 2 (Safety and immunogenicity assessment in infants)

Primary

- To assess the immunogenicity of the rotavirus vaccine after any dose in the study vaccine groups (infants aged 6-14 weeks).

Secondary

- For each viral concentration, to assess the safety and reactogenicity of two/three oral doses of the rotavirus vaccine *versus* placebo.
- To assess viral shedding in a subset of subjects.

Background of the Project including Preliminary Observations

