The active ingredient in RIX4414 is based on the human rotavirus strain 89-12. The 89-12 HRV was obtained from the stool of a 15-month-old infant with mild rotavirus diarrhea in December 1988 in Cincinnati (USA). The 89-12 strain belongs to the serotype G1P1A and genotype P8. A two-year prospective study showed that natural infection with such strains circulating in this community during 1988 and 1989 provided protection against subsequent illness and against re-infection during a two year follow up, since none of the children infected with the strain developed another episode of rotavirus diarrhoea (Bernstein et al., 1991). The strain was developed as a vaccine by the Virus Research Institute (VRI), now called AVANT, a biotechnology company in the US. The initial isolate was passaged in primary African Green Monkey Kidney cells (AGMK), and then further passaged on an approved AGMK cell line to produce initial clinical lots of vaccine based on uncloned P33 89-12 HRV strain. It was passaged in tissue culture using approved cell lines and was found to be attenuated when administered to volunteers. Clinical studies in US children and infants demonstrated the safety, immunogenicity and

efficacy of the vaccine in infants (Bernstein et al., 1998; Bernstein et al., 1999). A phase 2b trial with two doses of 10^5 ffu of 89-12 in US infants demonstrated 89% protection against any rotavirus gastroenteritis and even higher protection against severe rotavirus gastroenteritis during the first year after vaccination (Bernstein et al., 1999). In the second year the efficacy was 65%. The overall efficacy for 2 years was 76% against any rotavirus infection and 84% against severe rotavirus and 100% against any very severe rotavirus (Bernstein et al, 2000). Table 1 presents summary results of the studies conducted with rotavirus 89-12 strain.

Table 1: Summary results of the studies conducted with human rotavirus 89-12 strain

Country (reference)	Sample size	Age group	Side-effects		Immunogenicity	Efficacy (95% CI)
			Vaccine	Placebo		
USA (Bernstein et al, 1999)	215	10-16 weeks	Temperature 38.1°C- 38.5 °C - 19% 38.6°C- 38.9 °C - 6% ≥ 39.0- 4%	5% 2% 1%	Immune response to vaccinees 94.4%, placebo 3.8%	89% (65-96%)
USA (Bernstein et al, 1998)	34	Adults	Fever (>38°C) - 0 Diarrhoea- 1	0 0	Serum antibody rise to vaccinees 2, placebo 0	Not done
	40	2-12 years	Fever (>38°C) - 0 Diarrhoea- 1	0 0	Serum antibody rise to vaccinees 4, placebo 0	

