- Serum specimens will be collected at each study visit and 4 weeks after the last dose from all subjects only in part 2.
- Data collection will be by conventional paper case report forms (CRF's).

Sample size considerations

During the first phase of the study (immunization of children 2-4 years of age), the outcome of interest is reactogenicity. Even if intussusception were to occur with a relative risk similar to that observed with RRV-TV, we do not expect to observe intussusception with the small numbers included in this Phase I study. We will however use fever as a measure of reactogenicity. Based on previous studies in the USA involving active surveillance, we expect a background rate of 5% of fever (among placebo recipients). With 90 subjects (30 with $10^{5.0}$ ffu, 30 with $10^{6.0}$ ffu and 30 placebo), we will have 80% power ($p=0.05$) to detect a 35% incidence of fever among vaccinated subjects (assuming a background rate of 5% among controls). The same sample size assumptions hold true for the infant study.

For the second part involving both safety and immunogenicity, the primary outcome measure of interest is immunogenicity, although through this and all subsequent studies, reactogenicity will continue to be monitored. With 136 vaccinees in each vaccine group ($10^{5.0}$ 2 doses, $10^{5.0}$ 3 dose, $10^{6.0}$ ffu 2 doses) and 68 subjects receiving placebo, we will be able to detect a difference in take rates of 15% between the two dose levels (70% vs. 85%). The sample size will be sufficient to detect a difference in take rates of 12% (75% vs. 87%) between 2 doses of $10^{5.0}$ ffu and $10^{6.0}$ ffu. We are also assuming that 35% of infants will be exposed to wild type rotavirus during the 8 week study period and our numbers will be sufficient to differentiate a take rate between vaccine responses and background responses. If the proportion among controls is actually lower, and 70% of children have a four-fold rise in serum antibody titer, then the number of subjects required to achieve significance will be lower.

Study Cohort

Numbers of subjects / centres: Field workers will identify children of appropriate age, inform families of the purpose and scope of the study and offer participation. It is planned to vaccinate 10-12 children daily, and first dose of vaccines are expected to be complete within 2 weeks of the start of the study.

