Inclusion criteria for enrollment: Male or female, between 24 months and 48 months of age at the time of the first dose of vaccine for participation in the study part assessing the vaccine in toddlers. Male or female, between 6 and 14 weeks of age at the time of the first dose of vaccine for participation in the study part assessing the immunogenicity and safety of the vaccine in infants. Written informed consent, free of chronic or serious medical condition as determined by history and physical exam within 3 days of the first dose of vaccine, plan to stay in community for at least 3 months.

Exclusion criteria for enrollment: Malnutrition (<-2Z score weight for age), fever (>38°C), acute or chronic illness, use of antimicrobial drug within previous 14 days, hypersensitivity to any of the vaccine components (vaccine composition in **annex III**), use of any investigational drug during previous 30 days, any uncorrected congenital malformation of the gastrointestinal tract, use of any immunosuppressing drugs during the last 14 days (likelihood is remote), any evidence by physical exam of immunosuppressing condition, administration of gamma globulin or any other blood product, previous intussusception or abdominal surgery, known pregnant person in the home.

Elimination criteria during study: If an exclusion criteria develops while participating in the study, the subject will be eliminated from the study.

Definitions:

Fever: Rectal temperature > 38°C

Diarrhoea: Three or more looser stools than normal stools in a 24 hour period.

Contraindications to vaccination: Not applicable.

Conduct of the study: The study will be conducted according to Good Clinical Practices, the Declaration of Helsinki, and local rules and regulations of Bangladesh and the ICDDR,B. It will be reviewed and approved by the Ethical Review Committee (ERC) of the ICDDR,B prior to starting the study. The ERC is a recognized committee for review of research protocols involving humans and has a Multiple Project Assurance (MPA) with a US agency (USAID).

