- On day 42, insure that all concomitant medication taken during the study have been recorded.

Day 43 to 6 months.

- Monthly active surveillance to complete 6 months of followup. With each visit, inquire about symptoms or illnesses among subjects.
- At end of 6 months, terminate subject from the study

For infants(Part 2)

Day 0 (Visit 1)

- Same procedures as performed for toddlers in part 1.
- Obtain a blood sample for serology
- Prepare study vaccine and administer dose 1
- Collection of stool sample for rotavirus antigen by ELISA

Day 3, 7, 14, and 21 (first 150 subjects only)

- Collection of stool sample for rotavirus antigen by ELISA

Day 1-day 27

- Carry out active surveillance with all subjects by visiting house daily for 2 weeks and thereafter twice weekly. Measure rectal temperature daily. Use daily form to record symptoms or lack of symptoms. Have physician available at clinic and inform family of subjects that the physician is available should there be any illness during the time of the study. If subjects are brought to the clinic, record all symptoms in patient medical records. These medical records will be the source documents for the passive surveillance.

Day 28

- Insure that subject is eligible for dose 2 according to inclusion and exclusion criteria
- Obtain a serum blood sample for serology
- Prepare study vaccine and administer dose 2
- Collection of stool sample from subjects (first 150 only) for rotavirus antigen by ELISA

Day 29 – day 42

- Carry out active surveillance with all subjects by visiting house daily for 2 weeks. Measure rectal temperature daily. Use daily form to record symptoms or lack of symptoms. Have physician available at clinic and inform family of subjects that the physician is available should there be any illness during the time of the study. If subjects are brought to the clinic, record all symptoms in patient medical records. These medical records will be the source documents for the passive surveillance.

Day 31, 35, 42, 49 (first 150 subjects only)

- Collection of stool sample for rotavirus antigen by ELISA

Day 43-day 55

- Twice weekly active surveillance inquiring about symptoms or illnesses among subjects.

Day 56

- Insure that subject is eligible for dose 3 according to inclusion and exclusion criteria

- Obtain a serum blood sample for serology
 - Prepare study vaccine and administer dose 3
 - Collection of stool sample from subjects (first 150) for rotavirus antigen by ELISA
- Day 57-day 70

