Baseline characteristics of the subjects receiving vaccine and placebo will be examined for group comparability. Any significant baseline differences will be controlled for during data analysis. The frequency distribution will be examined to assess the distribution of data. Proportion of infants with adverse events will be compared between the different groups (vaccine, placebo, different doses and viral concentrations). Proportion of subjects that shed rotavirus at different time periods will be compared. Serological measures (proportion with ≥ 4 -fold increase in titer and geometric mean titer) will be compared between different viral concentrations/ doses and placebo recipients.

The proportions will be compared using χ^2 -tests and rate ratios (95% confidence intervals). The geometric mean titers (GMT) will be compared using non-parametric tests. Multivariate analysis will be done to simultaneously adjust for different factors.

Ethical Assurance for Protection of Human Rights

Describe in the space provided the justifications for conducting this research in human subjects. If the study needs observations on sick individuals, provide sufficient reasons for using them. Indicate how subject's rights are protected and if there is any benefit or risk to each subject of the study.

Human rotavirus vaccine (RIX4414), designed for preventing rotavirus will be evaluated among young children since the risk of the disease is greatest in that age group. Infants will be enrolled after their parents have been given a full explanation of the study and they have understood the implications of participating in this study, and have agreed to participate in writing. The study will be conducted according to Good Clinical Practices, the Declaration of Helsinki, and local rules and regulations of Bangladesh and the ICDDR,B.

The investigator and his staff will be aware of the possible increased risk of intussusception and will consider this diagnosis among children presenting symptoms of intussusception. The investigator and his staff will take appropriate actions to evaluate and treat the condition. A child with suspected intussusception will be referred to a local hospital in Dhaka (Children's hospital, Shishu Hospital). The hospital has the experience and capacity for diagnosis, non-surgical and surgical management of intussusception, and a pediatric surgeon at this hospital is a co-investigator on the protocol to assume

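### The dose comparison of 4-fold IgA rises is planned without stratifying by Day 0 IgA status, so infants already positive at entry can dilute it

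*Protocol*

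**What the plan says.** - **Endpoint and test (Data Analysis).** "Serological measures (proportion with ≥ 4 -fold increase in titer and geometric mean titer) will be compared between different viral concentrations/ doses"; placebo is a further comparator. Proportions are to be compared by chi-square tests and rate ratios with 95% confidence intervals. The section also promises control for significant baseline differences and a multivariate analysis, but it names no factors and does not mention Day 0 IgA.
- **Entry (Study Cohort, inclusion criteria).** Infants are "between 6 and 14 weeks of age at the time of the first dose of vaccine for participation in the study part assessing the immunogenicity". The exclusion list contains neither earlier rotavirus infection nor baseline IgA.
- **Baseline serum (Outline of study procedures, infants, Day 0).** "Obtain a blood sample for serology" is listed ahead of preparing and giving dose 1.
- **Sample size considerations.** "With 136 vaccinees in each vaccine group", the stated detectable differences are 70% versus 85% and 75% versus 87%. The only wild-type figure is "We are also assuming that 35% of infants will be exposed to wild type rotavirus during the 8 week study period".
- **Source of the planning rate (Response to external Reviewers' comments, Reviewer # 2, item 5).** An earlier rotavirus vaccine gave a 4-fold or greater IgA rise in 75% of Bangladeshi vaccinees aged 6 to 14 weeks, and this was considered in the sample size. No restriction by serostatus is mentioned.

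**The concern.** A 4-fold rise is measured against the infant's own starting titre. An infant whose IgA is already raised by natural infection starts high and is less likely to reach that threshold, whatever the concentration or number of doses. Such infants pull every vaccine arm down and narrow the differences between arms. Randomisation balances them but does not remove the dilution, so an adjustment triggered by baseline imbalance would not address it.

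Part 2 is meant to choose the concentration and regimen for later trials. A flattened dose response could be read as equivalence of the regimens, or a low take as poor vaccine performance, when part of the cause is infection before entry. The sample that identifies these infants is already being taken.

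**Working it through.** **1. The plan's own figure.** Power and alpha are stated only for the fever calculation (80%, 0.05) and are assumed here for Part 2. Sidedness is not stated.
- 70% versus 85%, two-sided: 121 per arm, or 134 with continuity correction. This matches 136; power at 136 is 85%.
- 75% versus 87%: 132 per arm one-sided and 167 two-sided. At 136, two-sided power is about 72%.

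So 72% is the two-sided reference for 75/87 before any dilution.

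**2. Dilution formula.** Let *s* be the share pre-exposed (taken as IgA-positive at Day 0), *r* their rise rate and *p* the take in Day 0-negative infants. The all-infant take in an arm is (1 − s)p + s·r. If *r* is the same in both arms, the difference shrinks by the factor (1 − s).

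*Inputs.* n = 136 and 75/87 come from the protocol. *s* = 5 to 20% is an assumption. *r* = 10% is also an assumption, loosely suggested by Table 1, where a US sample of 40 aged 2 to 12 years had "Serum antibody rise to vaccinees 4, placebo 0" (number vaccinated not given).

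**3. If 75/87 are rates in Day 0-negative infants (r = 10%).**
- s = 5%: 0.95×0.75 + 0.05×0.10 = 71.8%; 0.95×0.87 + 0.005 = 83.2%
- s = 10%: 0.90×0.75 + 0.10×0.10 = 68.5%; 0.90×0.87 + 0.01 = 79.3%
- s = 20%: 0.80×0.75 + 0.20×0.10 = 62.0%; 0.80×0.87 + 0.02 = 71.6%

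Power, two-sided 5%. The unstratified and Day 0-negative columns are exact enumerations of the uncorrected chi-square test; the stratified column is a simulated Mantel-Haenszel test in all infants.

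| s | Difference | Unstratified, n = 136 | Stratified, n = 136 | Day 0-negatives only (n) |
|---|---|---|---|---|
| 5% | 11.4 points | 62% | 69% | 70% (129) |
| 10% | 10.8 points | 53% | 65% | 68% (122) |
| 20% | 9.6 points | 39% | 56% | 63% (109) |

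With r = 25%, unstratified versus stratified power is 55% versus 62% at s = 10%, and 41% versus 51% at s = 20%.

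**4. If 75/87 are all-infant rates (r = 10%).** Solve p = (q − s·r)/(1 − s), where q is the all-infant rate.
- s = 5%: p = (0.75 − 0.005)/0.95 = 78.4% and (0.87 − 0.005)/0.95 = 91.1%
- s = 10%: p = (0.75 − 0.01)/0.90 = 82.2% and (0.87 − 0.01)/0.90 = 95.6%

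Unstratified power stays at 72%. Stratified power is 81% at s = 5% and 91% at s = 10%. At s = 20% the upper rate would be (0.87 − 0.02)/0.80 = 106%, which is impossible, so this reading caps *s* below 20%.

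**5. If pre-exposed infants show the same dose difference (say 50% versus 62%).** Power at s = 10% is 68% unstratified, 69% stratified and 68% in Day 0-negatives only. At s = 20% it is 65%, 67% and 63%. Stratifying does no harm; restricting the set loses a little at the larger share.

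**The case against.** **This belongs in an analysis plan.** Analysis sets and stratification factors are often left there, and the multivariate clause could include Day 0 IgA. That is fair as far as it goes. But this protocol itself fixes the endpoint, the groups and a chi-square test, and it sizes the trial on take rates without saying which infants they describe. Unnamed factors do not commit the analysis to Day 0 IgA.

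**The assumed 35% means a large share is already infected at entry.** A reader might infer this by running 35% per 8 weeks back to birth: 1 − 0.65^(6/8) = 28% at 6 weeks and 1 − 0.65^(14/8) = 53% at 14 weeks. The documents do not support it. The 35% is assumed exposure during the study and serves the comparison with background responses. A constant hazard from birth is nowhere stated, and the Background expects considerable maternal antibody at this age. If pre-exposed infants showed no rise, 28% would cap take at 72%, below the 75% reported for this age group (with a different vaccine). These figures are not used here.

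**Pre-exposed infants cannot respond.** A reader might infer this too. The Background calls re-infections frequent, and the Table 1 count is weak evidence: its denominator is unclear, and rises were also far from universal in samples aged 6 to 26 weeks (2 in a sample of 9, 19 in a sample of 42). Less likely to show a rise is as far as the argument goes.

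**An all-infant comparison is legitimate.** This stands. The aim is a regimen for Bangladeshi infants generally, and restricting the primary set to Day 0-negatives is a trade-off. For that reason the primary set should remain all infants, with stratification.

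**Conclusion.** The point holds in a limited form. As written, the comparison makes no committed use of Day 0 IgA status. If some infants are positive at entry and rise less often, it gives up power that a stratified test on the same data would recover. In the illustration with 10% pre-exposed, stratifying moves power from 53% to 65%, or from 72% to 91% if the planning rates already describe all infants. Stratified power was at least as high in each scenario shown.

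The size depends on two quantities the protocol does not give: the share positive at Day 0 and their rise rate. It would be too strong to conclude that the trial is underpowered for this reason. The 75% planning rate came from infants of the same age with no stated serostatus restriction, so the dilution may already be inside it, and in that case the planned power is not lost.

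**What to change.** - **Data Analysis.** Make the primary comparison of take (4-fold or greater IgA rise) a Mantel-Haenszel analysis in all infants, stratified by Day 0 IgA status (positive or negative by the assay cut-off, which should be stated). Report the Mantel-Haenszel rate ratio with its 95% confidence interval, in keeping with the rate ratios already planned. Prespecify take in Day 0 IgA-negative infants as a supporting analysis.
- **Sample size considerations.** State whether 70/85 and 75/87 refer to all infants or to Day 0-negative infants. If the latter, give the expected number per arm.

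The cost is a few sentences. No visit, sample or assay is added, and randomisation is unchanged. Day 0 status is fixed before dose 1, so the strata cannot be influenced by treatment.

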Describe explicitly the plans for disseminating the accomplished results. Describe what type of publication is anticipated: working papers, internal (institutional) publication, international publications, international conferences and agencies, workshops etc. Mention if the project is linked to the Government of Bangladesh through a training programme.

The findings from this study will be published in internal publications and peer reviewed journals, and disseminated in national and international conferences.

Collaborative Arrangements

Describe briefly if this study involves any scientific, administrative, fiscal, or programmatic arrangements with other national or international organizations or individuals. Indicate the nature and extent of collaboration and include a letter of agreement between the applicant or his/her organization and the collaborating organization. (DO NOT EXCEED ONE PAGE)

TRAVEL COSTS						
International travel						20,000
Investigator Meeting						5,000
Local transportation cost						5,000
SUB-TOTAL:						30,000
SUPPLIES & OTHER COSTS						
Office rent, communications and utilities						10,000
Mobile phone						1,500
Drugs						1,000
Office & field supplies						1,500
Printing & Publications of forms						10,000
Spoon, cups, cylinder etc.						750
Needles, Syringes, thermometers, etc.						8,000
Furniture						1,500
Cold pack						100
Lab supplies cost						4,000
Shipping cost for sending specimen						10,000
Cost for safety monitoring Comm						1,000
Cold box (4)						250
Publications						500
Hospitalization/Attend cost (Shishu Hospital)						2,050
Service charges (Shishu Hospital)						
- [name]			15	5%	100	1,500
- Medical Officer			15	15%	30	450
SUB-TOTAL:						54,100
INTER-DEPARTMENTAL SERVICES						
Repair & maintenance						500
Transport (land)						4,000
Specimen handling fees						5,000
IgA ELISA@4X3X525	4	4	576			9,216
RV [contact]	3.3	1	2430			8,019
Culture RV						5,000
Typing RV (G/P/Electropherotyping)						6,000
Medical Illustration						500
Mimeography, Library charge etc.						500
SUB-TOTAL:						38,735
CAPITAL ITEMS						
Computers (2)/printer/UPS/accessories etc.						5,000
Gel electrophoresis apparatus						3,000
Refrigerator (1)						1,000
Freezer						6,000
SUB-TOTAL						15,000
TOTAL DIRECT COSTS:						319,870
OVERHEAD @25%						79,968
TOTAL PROJECT COSTS:						399,838

[name] 31.5.24
[name]
 Senior Budget & Cost Officer
 ICDDR, B, [name]
 [name], Bangladesh.

Budget Justifications

Please provide one page statement justifying the budgeted amount for each major item. Justify use of man power, major equipment, and laboratory services.

Budget justification

Briefly relate each item in the budget (personnel, supplies, equipment, animals, patient costs, travel, etc.) to the activities outlined in the research proposal

The total duration of the proposed study will be of 15 months. The study involves recruitment of study subjects, either one or two or three doses of vaccination to about 566 healthy children (toddlers and infants), follow up at their homes and collection of blood and stool specimens.

Investigators: The amount budgeted for the investigators reflects a reasonable estimate of the minimum time required to implement the study. [name], PI of the study will be responsible for overall implementation of the study. Drs. [name] and [name] will provide advice on epidemiological aspects, [name] on clinical aspects while Drs. [name] and [name] will be responsible for laboratory methods. [name] (Shishu hospital) will examine suspected cases of intussusception and will take appropriate measures. Medical Officer (Shishu) will assist the Paediatric surgeon for the management of referred cases. [name] and [name] will provide overall guidance of the study.

Research Investigator will coordinate all clinical and administrative activities.

Medical officer will be based in the clinic and be responsible for examination of the subjects, recruitment and vaccination. S/he will provide necessary treatment.

Senior staff nurse: will assist medical officer in examining patients and collection of specimens. Responsible for dispensing medicines (if required).

Field Research Assistants/attendants: Inform families of the purpose and scope of the study, offer participation and bring subjects to their clinic.

Data Manager/ Programmer: Overall data management and designing systems for analysis of data.

Data entry technician: entry of data

Senior Lab attendant: Collection and recording of samples.

Office manager: ensure overall logistics.

Consultant: Advise and guide for smooth running of the project.

GCP monitor: will check Case Report Forms (CRFs) for completeness and correspondence with source documents, monitor regulatory files and validate data files in computer.

Supplies

Computers: Two computers (one for data entry and analysis and other to be used by project office manager/Admin Asst) will be required.

Mobile phone: To communicate with the field staff for any adverse events and referral of patients.

Gel Electrophoresis apparatus: For typing of rotavirus.

Refrigerator/cold box: Keeping and transportation of specimens.

Laboratory tests: ELISA, Culture and typing for identification of rotavirus.

Transport costs: To visit families, bringing of subjects and transport cost of the families.

Hospitalization cost: Treatment cost for any hospitalized cases.

Office rent: Cost for renting the clinic

International travel: Consultation meeting with other RV partners

Other Support

Describe sources, amount, duration, and grant number of all other research funding currently granted to PI or under consideration. (DO NOT EXCEED ONE PAGE FOR EACH INVESTIGATOR)

Principal Investigator of the study " Epidemiology and surveillance of multidrug resistant Mycobacterium tuberculosis and assessment of directly observed therapy short course (DOTS) programme in selected areas of Bangladesh"
Funded by USAID, Amount: US\$ 577, 604

Follow-up of intussusception cases

In light of the possible increased risk of intussusception following administration of a previously licensed rotavirus vaccine, the safety of the candidate HRV vaccine will be monitored vigilantly during the clinical studies.

The investigator will be asked to inform the parents/guardians of the signs and symptoms of intussusception. Parents/guardians/caretakers of study subjects will be asked to contact the investigator if they notice any signs or symptoms indicative of intussusception. Symptoms consistent with intussusception are severe colicky abdominal pain, persistent vomiting, bloody stools, abdominal bloating and fever up to 41°C. The investigator will be aware of the possible increased risk of intussusception and will consider this diagnosis among children presenting these symptoms. The investigator and his staff will take appropriate actions to treat the condition. Child with suspected intussusception will be referred to a local hospital in Dhaka (Children's hospital, Shishu Hospital). The hospital has the experience and capacity for diagnosis, non-surgical and surgical management of intussusception.

If any case of intussusception should occur during this clinical study, the following procedures will be followed by the investigator for work-up of the intussusception cases.

Case ascertainment

The diagnosis of intussusception should be documented by radiography. Documentation by ultrasonography will be optional depending on availability of necessary expertise.

Data collection for intussusception cases

The investigator will document all available information regarding any intussusception cases occurring during the clinical studies on the Serious Adverse Event pages and fax within 24 hours (1 calendar day) of his/her becoming aware of the event to the GSK Biologicals Contact for Serious Adverse Event (SAE) Reporting.

The investigator should follow the same procedures for reporting intussusception cases as for other SAEs. To allow for a complete assessment of the intussusception cases, information on the subject's feeding practices, immunisation history, as well as any other information thought necessary for assessment by the study staff should be reported to the SB safety contact *by using the IS reporting form*.

Serum, throat and stool specimen will be collected from intussusception cases

Idiopathic intussusception is thought to be related to lymphoid hyperplasia in the intestinal sub-mucosa and/or mesenteric adenitis resulting from infections. Infectious agents most clearly linked to intussusception are enteroviruses and respiratory adenoviruses. Human rotaviruses also may cause intussusception, although epidemiological data suggest this must be very unusual. In theory, any agent able to replicate in the small intestine could provoke this condition.

GSK will use a central laboratory to perform RT-PCR on throat swabs and stool samples for enteroviruses and adenoviruses and on stool samples alone for rotaviruses. The physician treating a case of intussusception should submit stool samples to the hospital microbiology laboratory for culture of enteric pathogens such as *Salmonella*, *Shigella*, *Campylobacter*, and *Yersinia*. If culture results suggest presence of enteropathogenic *E. coli*, representative colonies should be retained for further evaluation. The samples to be collected and their handling are described below

If possible a stool specimen should be collected just prior to as well as samples 24 hours and 48 hours after the reduction. The hospital microbiology laboratory should divide each stool specimen into an aliquot for its own testing and two additional aliquots of at least 2 grams each to be frozen at -20°C to -70°C. The frozen stool samples will be used for RT-PCR and other studies to be arranged by GSK Biologicals, such as virus culture, antigen detection by immunoassay, or electron microscopy for virus-like particles.

Accordingly, a complete set of stool specimens will be comprised of 3 specimens submitted for bacterial culture and 6 frozen specimens retained for shipment to GSK Biologicals. In the event that faeces are unobtainable at any of the requested sampling times, 3 separate rectal swab specimens should be collected.

One swab specimen should be submitted for bacterial culture and the other 2 swabs should be placed each in a separate tube of 2 ml of sterile virus transport media and frozen at -20°C to -70°C .

A throat swab should be collected as soon as possible after intussusception is diagnosed. The throat swab should be placed in 2 ml of sterile virus transport media and frozen at -20°C to -70°C .

In case of surgical reduction, a surgical specimen of any enlarged mesenteric lymph will be obtained. If bowel or the appendix is resected, these specimens also should be included in the evaluation. If possible, resected tissue should be divided into 3 aliquots to be processed for routine fixation, for electron microscopy (fixation in 4% paraformaldehyde and 1% glutaraldehyde), and for frozen sectioning for detection of virus antigens by immunofluorescence. Routinely fixed specimens should be examined for histopathologic evidence of acute inflammation and presence of virus inclusions or other diagnostic signs. Additional testing including referral of tissue blocks for outside review and/or tests using immunohistochemistry, in situ hybridisation, or PCR will be arranged by GSK Biologicals in consultation with the Attending Pathologist.

Acute and convalescent blood (at least 2 ml of each) will be collected and stored at -20°C for serologic testing. These specimens will be supplemented by antecedent serum specimens from the patient already collected under this protocol. Testing will be arranged by GSK Biologicals to detect an acute antibody response to any pathogen identified by stool and/or throat swab tests or by histopathologic evaluation of tissue.

